10.2.2. Study discontinuation

Table 10.2.4 Study discontinuation.

Reason	N	%
Never treated* ¹		
Withdrawal of consent		
Death (due to toxicity)* ²		
Death (non-treatment-related) * ³		
Lost to follow-up		
Other * ⁴		
Total		

(*¹) See [Listing 10.1.5](#); (*²) Cause of death = Study drug related AE or UK relationship; (*³) Cause of death = Malignant disease, Non study drug related AE or Other; (*⁴) Specified in [Listing 10.2.5](#).

Listing 10.2.5 Study discontinuation due to other reason.

Patient id.	Specify

10.3. Protocol Deviations

Protocol deviations of “All included patients” population will be shown.

Listing 10.3.1 Protocol deviations.

Patient id.	Deviation type	Description

11.Efficacy Evaluation

11.1. Demographic and Other Baseline Characteristics

Demographic and other baseline characteristics of “All Included Patients” population will be shown.

11.1.1. Patient Characteristics at Baseline

Table 11.1.1 Baseline characteristics.

	N	%
Number of patients		
Gender		
Female		
Male		
Age		
Median (range)		
Mean (StD)		
Age group		
18-49		
50-69		
≥70		
Race		
American Indian or Alaska Native		
Asian		
Black or African American		
Native Hawaiian or Other Pacific Islander		
White		
Other (specify)*		

(*) See [Listing 11.1.2](#).

Listing 11.1.2 Race (other).

Patient	Race	Specify

11.1.2. Disease at diagnosis and current disease

Table 11.1.3 Disease at diagnosis and current disease.

	N	%
Time from first diagnosis to first infusion		
Median (range)		
Mean (StD)		
Primary tumor side		
Right		
Left		
Primary tumor site		
Cecum		
Ascending		
Transverse		
Descending		
Sigmoid		
Rectum		
...		
Histology grade		
G1. Well differentiated		

	N	%
G2. Moderately differentiated G3. Poorly differentiated G4. Undifferentiated GX. Grade cannot be evaluated		
KRAS mutational status Wild type Not done UK Mutated, specify* ¹		
NRAS mutational status Wild type Not done UK Mutated, specify* ²		
BRAF mutational status Wild type Not done UK Mutated, specify* ³		
MSI status Done Not done/UK MSI phenotype* ⁴ MSI Stable MSI-H MSI-L		
Stage at diagnosis I ...		
TNM ...		
Dukes A B ...		
MAC A B1 ...		

(*¹) See [Listing 11.1.4](#) (*²) See [Listing 11.1.5](#) (*³) See [Listing 11.1.6](#) (*⁴) [Listing 11.1.7](#).

Listing 11.1.4 KRAS mutational status (mutated).

Patient	Specify

Listing 11.1.5 NRAS mutational status (mutated).

Patient	Specify

Listing 11.1.6 BRAF mutational status (mutated).

Patient	Specify

Listing 11.1.7 MSI phenotype (gene affected).

Patient	MSI phenotype (MSI Stable/MSI-H/MSI-L)	Gen affected

Table 11.1.8 Current disease.

	N	%
Current disease status		
Locally recurrent disease		
Metastasis		
Both		
Time from diagnosis of advanced disease to study entry		
Median (range)		
Mean (StD)		
Time from prior last progression before study entry		
Median (range)		
Mean (StD)		
Time from stop date of prior chemotherapy to study entry		
Median (range)		
Mean (StD)		
Site of current disease		
Primary tumor site/ Local relapse		
Lung		
...		
Number of sites involved		
1		
2		
...		
Median (range)		
Mean (StD)		

11.1.3. Prior Relevant Medical History

Table 11.1.9 Prior medical history.

SOC	Preferred term	N	%
Patients with any past and/or concomitant disease or past surgeries			
Gastrointestinal disorders	Constipation		
	Diarrhoea		
	...		
...	...		
...	...		

Listing 11.1.10 Prior medical history (ongoing events).

Patient id.	Description (Literal)	SOC	PT	Onset date

11.1.4. Prior Anticancer Therapy

Table 11.1.11 Prior surgery (major surgical procedures for study disease only).

	N	%
Surgery (Y/N)		
Residual disease		
Yes		
No		
UK		

Table 11.1.12 Prior radiotherapy.

	N	%
Radiotherapy (Y/N)		
Type		
External		
Brachytherapy		
IORT		
IMRT		
Intention		
Curative		
Palliative		
Concurrent		

Table 11.1.13 Prior anticancer medical therapy.

	N	%
Number of prior lines (including neo/adjuvant)		
1		
...		
Number of prior lines for advanced disease		
1		
...		
Number of prior agents (including neo/adjuvant)		
1		
...		
Number of prior agents for advanced disease		
1		
...		
Prior agents (ATC coded)		
Fluoropyrimidine		
Irinotecan		
Oxaliplatin		
...		
Last prior agents (ATC coded)		
...		
Progression free interval*		
Median (range)		
Progression free interval to Oxaliplatin		
Median (range)		
Best response to last prior therapy		
Complete Response		
Partial Response		
Stable Disease		
Progressive Disease		
NE/UK/NA		

(*) Time from last prior therapy to first infusion of PM60184.

11.1.5. Physical Examination and performance status

Table 11.1.14 Baseline ECOG Performance Status.

	N	%
ECOG PS		
0		
1		

Table 11.1.15 Baseline physical examination.

	N	%
Physical examination abnormalities (Y/N)		
Weight (kg) Median (range) Mean (StD)		
Height (cm) Median (range) Mean (StD)		
Body surface area (m ²) Median (range) Mean (StD)		
BMI (kg/m ²) Median (range) Mean (StD) ≤ 20 21-25 26-30 > 30		

11.1.6. Vital signs, Electrocardiogram, LVEF and other tests

Table 11.1.16 Vital signs, Electrocardiogram, LVEF and other tests.

	N	%
Vital signs Heart rate (Beats/minute) Median (range) Mean (StD) Systolic blood pressure (mmHg) Median (range) Mean (StD) Diastolic blood pressure (mmHg) Median (range) Mean (StD) Temperature (°C) Median (range) Mean (StD)		
ECG Normal Significant abnormalities Non significant abnormalities		
LVEF Method ECHO MUGA Result Normal Non-significant abnormalities Significant abnormalities		
Pregnancy test Positive Negative NA*		

(*) See [Listing 11.1.17](#).

Listing 11.1.17 Patients with not applicable pregnancy test.

Patient	Specify

Listing 11.1.18 Other tests/ procedures.

Patient	Test name	Result	Comments

11.1.7. Hematological Values at Baseline

Table 11.1.19 Hematological abnormalities at baseline*.

	Grade 1		Grade 2		Grade 3		Grade 4		Grade 1/4		Total
	N	%	N	%	N	%	N	%	N	%	
Anaemia											
Leukopenia											
Neutropenia											
Lymphopenia											
Thrombocytopenia											

(*) Defined as the last value recorded before or on the date of first infusion.

Table 11.1.20 Hematological values at baseline*.

	Median (range)
Hemoglobin (g/dL)	
WBC ($10^9/L$)	
Neutrophils ($10^9/L$)	
Lymphocytes ($10^9/L$)	
Platelets ($10^9/L$)	

(*) Defined as the last value recorded before or on the date of first infusion.

Listing 11.1.21 Hematological abnormalities at baseline* (grade >1).

Patient	Test	Grade

(*) Defined as the last value recorded before or on the date of first infusion.

Listing 11.1.22 Hematological tests not assessed at baseline*.

Patient	Test
...	
...	

(*) Defined as the last value recorded before or on the date of first infusion.

11.1.8. Biochemical Values at Baseline

Table 11.1.23 Biochemical abnormalities at baseline*.

	Grade 1		Grade 2		Grade 3		Grade 4		Grade 1/4		Total N
	N	%	N	%	N	%	N	%	N	%	
ALT increased											
AP increased											
AST increased											
Creatinine increased											

(*). Defined as the last value recorded before or on the date of first infusion.

Table 11.1.24 Biochemistry values at baseline*.

	Median (range)
ALT (IU/L)	
AP (IU/L)	
AST (IU/L)	
Creatinine (mg/dL)	
Creatinine Clearance (mg/min)	
Direct bilirubin (mg/dL)	
GGT (U/L)	
Glucose (mmol/L)	
K (mmol/L)	
LDH (IU/L)	
Na (mmol/L)	
Total bilirubin (mg/dL)	

(*). Defined as the last value recorded before or on the date of first infusion.

Listing 11.1.25 Biochemical abnormalities at baseline* (grade >1).

Patient	Test	Grade

(*). Defined as the last value recorded before or on the date of first infusion.

Listing 11.1.26 Biochemical tests not assessed at baseline*.

Patient	Test
...	
...	

(*). Defined as the last value recorded before or on the date of first infusion.

Table 11.1.27 Other metabolic abnormalities at baseline*.

	Grade 1		Grade 2		Grade 3		Grade 4		Grade 1/4		Total N
	N	%	N	%	N	%	N	%	N	%	
GGT increased											
Hypercalcemia ^{*2}											
Hyperglycemia											
Hyperkalaemia											
Hypertatremia											
Hypoalbuminaemia											
Hypocalcemia ^{*2}											
Hypoglycemia											
Hypokalaemia											
Hyponatremia											

(*). Defined as the last value recorded before or on the date of first infusion.

(*²) Total plasmatic calcium corrected by albumin.

Listing 11.1.28 Other metabolic abnormalities at baseline* (grade >1).

Patient	Test	Grade

(*) Defined as the last value recorded before or on the date of first infusion.

11.1.9. Signs and Symptoms at Baseline

Table 11.1.29 Signs and symptoms at baseline*.

	N	%
No. of signs and symptoms per patient		
0		
1		
2		
≥ 3		
Median (range)		
Mean (StD)		
No. of disease related signs and symptoms per patient		
0		
1		
2		
≥ 3		
Median (range)		
Mean (StD)		

(*) AEs with onset day previous to first administration of the study treatment.

Table 11.1.30 Signs and symptoms at baseline.

MedDRA SOC/PT*	N	Grade 1		Grade 2		Grade 3		Grade 4		Grade 1/4	
		N	%	N	%	N	%	N	%	N	%
Constipation											
Diarrhoea											
Dyspnea											
Pain											
...											

(*) Sorted by frequency.

Table 11.1.31 Disease related signs and symptoms at baseline.

MedDRA SOC/PT*	N	Grade 1		Grade 2		Grade 3		Grade 4		Grade 1/4	
		N	%	N	%	N	%	N	%	N	%
Constipation											
Diarrhoea											
Dyspnea											
Pain											
...											

(*) Sorted by frequency.

Listing 11.1.32 Signs and symptoms at baseline.

Patient	Sign/symptom	Grade	Onset date	Relationship	Treated

(*) Those events with grade ≥ 2 or with relationship='Prior tumor treatment' will be highlighted.

11.1.10. Peripheral Neuropathy

Table 11.1.33 Peripheral neuropathy.

	N	%
Peripheral neuropathy (Y/N)		
Type of peripheral neuropathy		
Sensory		
Motor		
Both		
Location		
Hands		
Feet		
Arms		
Legs		
...		
Worst grade observed (NCI-CTCAE v.4)		
Grade 1		
Grade 2		
Grade 3		
Grade 4		
UK		
Outcome of the overall grade		
Complete recovery		
Recovered with sequelae		
Neuropathy due to prior chemotherapies or biological treatments: agents		
Oxaliplatin		
Other		
Neuropathy due to prior chemotherapies or biological treatments: dose modification / discontinuation		
Yes		
No		
UK		

11.1.11. Concomitant Therapy and Procedures at Baseline

Table 11.1.34 Concomitant medication at baseline (ATC1/ATC2/ATC4/PN).

Concomitant medication at baseline	N	%
Alimentary tract and metabolism		
Antacids		
Magnesium compounds		
Magnesium adipate		
...		
Blood and blood forming organs		
Antithrombotic agents		
Vitamin K antagonists		
Acenocoumarol		
...		

Table 11.1.35 Summary of concomitant medication at baseline.

	N	%
No. of systems at BL (ATC1 level)		
0		
1		
2		
≥ 3		
Median (range)		
Mean (StD)		
No. of indications at BL (ATC2 level)		
0		
1		
2		
≥ 3		
Median (range)		
Mean (StD)		
No. of agent families at BL (ATC4 level)		
0		
1		
2		
≥ 3		
Median (range)		
Mean (StD)		
No. of agents at BL (PN level)		
0		
1		
2		
≥ 3		
Median (range)		
Mean (StD)		

Listing 11.1.36 Concomitant therapy.

Patient	Type	Agent/Procedure	Route	Daily dose	Units	Start date	Reason	Indication	Details	Start date of study drug administration

If there is a relevant number of patients receiving the same concomitant medication, a table summarizing this information might be added.

11.2. Measurements of Treatment Compliance

Compliance of individual patients with the treatment regimen under study will be measured and tabulated in Appendix I.12.1 and listed in Appendix III (ICH listings).

11.3. Efficacy Analysis

Efficacy analysis will be carried out on the “All Evaluable Patients” population except duration of response analysis which will be carried out on the “All Responding Patients” population and QoL analysis, which will be carried out on the “All evaluable QoL” population.

11.3.1. Primary Analysis

Patients who are evaluable for efficacy but have not been followed-up for at least 12 weeks (+/- 5 days) will be categorized as PFS3=No.

Table 11.3.1 PFS3 rate (binomial exact estimator and 95% confidence interval).

	Proportion	Lower 95% limit	Upper 95% limit
PFS3*			

(*) Progression-free-survival rate at 12 weeks (+/- 5 days).
Binomial exact estimator and 95% CI.

Listing 11.3.2 Censored patients.

Patient	PFS3 rate	PFS (months)	Reason for censoring

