*** Permitted windows for assessments before Day 1 of Cycle 1:**

If physical examination, ECOG PS, vital signs, hematology/biochemistry were assessed >10 days before Day 1 of Cycle 1, the tests must be repeated within 2 days before the first study drug administration.

If pregnancy test was done >7 days before Day 1 of Cycle 1, the test must be repeated within 2 days before the first study drug administration.

If tumor assessments were done >28 days before Day 1 of Cycle 1, the tests must be repeated within 2 days before the first study drug administration.

A patient should only be treated if eligibility criteria are still met according to assessments performed closest to treatment start.

Permitted windows for assessments after Day 1 of Cycle 1:

- 2 days for physical examination and ECOG PS (on Day 1) and for vital signs (on Days 1 and 8), always before study drug administration.

+ 7 days for tumor assessments (except in Week 12 when there is a maximum 5-day window).

± 2 days for Day 1 study drug administration (from Cycle 2 onwards).

± 2 days for Day 8 study drug administration.

- 2 days for laboratory tests. To confirm criteria for treatment continuation, laboratory assessments must be performed within 2 days prior to drug administration.

If a drug administration is delayed beyond the permitted protocol window, assessments planned for the original administration day must be repeated on the day the dose is finally administered.

1. EOT assessments should take place approximately 30 days (\pm 15 days) after the last drug administration or before starting new therapy. Loss to follow-up, or failure to attend the EOT visit due to a deteriorated clinical condition or due to personal reasons such as returning to their previous hospital, will not be considered protocol deviations.

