4. PATIENTS EVALUABILITY CRITERIA

Patients with relapsed, metastatic/locally advanced CRC with any KRAS-mutation status (wild-type, mutated, or status unknown), progressing after standard treatments (fluoropyrimidine, irinotecan, and oxaliplatin).

Patients must fulfill all the eligibility criteria to be eligible to participate in the study.

The study will include the following analysis population set definitions:

- “All Included Patients” analysis set is defined as all patients recorded in the database who have been included in the trial (excluding screening failures), independently of whether they have received the study drug or not.
- “All Treated Patients” analysis set is defined as all included patients who have received at least one (complete or incomplete) dose of the study drug.
- “All Evaluable Patients for Efficacy” analysis set is defined as all eligible patients who have at least one complete treatment cycle (or two PM060184 dose administrations over two cycles) and have, at least, one disease assessment at Week 6 and another one at Week 12. In addition, any patient who presents disease progression, symptomatic deterioration due to the disease or clinical progression, dies due to malignant disease, discontinues treatment due to unmanageable toxicity, or dies or discontinues treatment due to a treatment-related AE before evaluation of the response at Week 12 will also be considered evaluable for the primary endpoint and classified as a non-responder. Patients who have no disease assessment at Week 6 but remain on treatment and are assessed at Week 12 (or later, and with no evidence of disease progression) will be considered evaluable for efficacy. Patients who refuse further treatment before Week 12 due to reasons other than related AEs not considered unmanageable toxicity will be replaced.

- “All Responder Patients” analysis set is defined as all evaluable patients for efficacy who have had CR or PR as overall best response according to the RECIST v.1.1.
- “All Evaluable Quality of Life (QoL)” analysis set is defined as all patients who have fulfilled the EORTC-QLQ-C30 and EORTC-QLQ-CPIN20 questionnaires for at least two timepoints, one at baseline and at least one after the start of the therapy.

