Patients must be replaced if they are considered not evaluable for efficacy for the primary endpoint (PFS3), i.e., if they are withdrawn from the study due to significant clinical deterioration of unknown reason, hypersensitivity reactions, unrelated AEs without any tumor assessments after the start of study treatment, if they refuse further treatment before Week 12 due to reasons other than related AEs not considered unmanageable toxicity, if they receive less than one complete treatment cycle (at least two PM060184 dose administrations over two cycles unless treatment discontinuation was due to unmanageable toxicity), or do not have the disease assessment at Week 12 (except in the cases outlined above).

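### Treated patients with no Week-12 status and no listed failure event leave the PFS3 denominator and are replaced; no planned PFS3 rate counts them, so an all-treated sensitivity row is needed

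*SAP*

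**What the plan says.** The primary analysis set is the evaluable-for-efficacy set (SAP 4.2). SAP section 4 gives two main ways into it:

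- **By assessment.** The patient has had enough treatment and must "have, at least, one disease assessment at Week 6 and another one at Week 12". The Week-6 scan is waived for a patient who stays on treatment and is assessed at Week 12 or later.
- **By a listed failure before Week 12.** The events are progression (including clinical or symptomatic), death from the cancer, stopping for unmanageable toxicity, and death or stopping because of a related adverse event. Such a patient "will also be considered evaluable for the primary endpoint and classified as a non-responder".

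The same section replaces, among others, patients who "do not have the disease assessment at Week 12 (except in the cases outlined above"). Protocol 6.3.4 and 8.1 define evaluability and replacement in the same way.

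SAP 11.3.1 then adds a scoring rule, limited to patients evaluable for efficacy: those who "have not been followed-up for at least 12 weeks (+/- 5 days) will be categorized as PFS3=No".

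SAP 8.13 leaves missing values out of all calculations. SAP 6.2.2 plans one efficacy analysis in all treated patients, but it is of PFS as a time-to-event variable.

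**The concern.** A reader of SAP 11.3.1 alone could think that unknown Week-12 status is handled conservatively. The rule covers only patients who are already evaluable. A treated patient with neither a Week-12 (or later) assessment nor a listed failure is not evaluable, so the rule cannot reach that patient. This group includes patients lost to follow-up, patients who withdraw consent and patients whose scan was not done. They are removed and another patient takes their place.

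The trial is single-arm and open-label and is decided by a count. If patients who vanish before Week 12 do worse than those who stay, replacing them raises the observed PFS3 rate. A result at or just above 25/60 could then owe something to replacement, and no planned PFS3 rate would show how much.

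**Working it through.** **1. Can SAP 11.3.1 reach these patients?**

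| Patient before Week 12 | Evaluable (SAP 4)? | PFS3 score | Replaced? |
|---|---|---|---|
| Listed failure event | Yes | No, by SAP 4 itself | No |
| Progression-free at a Week-12 or later assessment | Yes | Yes | No |
| No assessment at Week 12 or later, no listed failure | No | None | Yes |

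The rule in 11.3.1 applies to the evaluable rows only. There it overlaps with the non-responder classification in SAP 4, and it may also settle a scan taken too early for the ±5-day window. The third row is outside it.

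**2. Does another analysis count the third row?** Not as a PFS3 rate. The all-treated PFS analysis (SAP 6.2.2, Table 11.3.7) includes these patients, but PFS runs to the last tumor evaluation when there is no event. They are censored unless progression or death is known.

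**3. The plan's own figures** (SAP 5.1 and 5.2): p0 = 0.30, p1 = 0.50, one-sided alpha 0.025, power 90%, at least 7 of 24 to continue, at least 25 of 60 for success.

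n = [1.960·√(0.30·0.70) + 1.282·√(0.50·0.50)]² / 0.20² = 59.2, rounded up to 60. This reproduces the stated size.

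The exact probability of declaring activity under the two-stage rule is

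P(p) = Σ over x from 7 to 24 of Bin(x; 24, p) · Pr[Bin(36, p) ≥ 25 − x].

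P(0.30) = 3.5% and P(0.50) = 91.8%. That 3.5% exceeds the nominal 2.5% is a separate matter of the cut-off. Here 3.5% is only the baseline.

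**4. Effect of replacement.** Let q be the fraction of treated patients lost in this way and s their true PFS3 rate. With 30% among all treated patients, the rate among evaluable patients is p = (0.30 − q·s)/(1 − q). Neither q nor s is in the documents; both are assumptions.

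| q | s = 0: p | P(active) | s = 0.15: p | P(active) | s = 0.30: p | P(active) |
|---|---|---|---|---|---|---|
| 0% | 30.0% | 3.5% | 30.0% | 3.5% | 30.0% | 3.5% |
| 2% | 30.6% | 4.5% | 30.3% | 4.0% | 30.0% | 3.5% |
| 5% | 31.6% | 6.3% | 30.8% | 4.8% | 30.0% | 3.5% |
| 10% | 33.3% | 10.8% | 31.7% | 6.4% | 30.0% | 3.5% |

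**5. Effect on a just-positive result.** For 60 evaluable patients, 5% lost means about 60/0.95 = 63 treated, and 10% lost about 60/0.90 = 67. Counting the extra patients as No, with exact (Clopper-Pearson) 95% CIs:

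- 25/60 = 41.7% (29.1–55.1)
- 25/63 = 39.7% (27.6–52.8)
- 25/67 = 37.3% (25.8–50.0)

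**The case against.** **An evaluable-patient primary set with replacement is a deliberate choice, stated consistently in both documents.** This stands. SAP 11.3.1 overlaps with SAP 4 but does not contradict it. A reader might infer that the rule was written for lost patients and has been disabled by mistake. The text does not show that, since the rule is limited in its own words to evaluable patients.

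**Much informative loss is already counted as failure.** This stands too. The listed events cover clinical and symptomatic progression, death from the cancer and toxicity stops without any Week-12 scan, so the residual group may be small. The Schedule of Assessments (footnote 12) and Protocol 7.6 also ask for the Week-12 evaluation in all patients without progression.

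**Three places might be taken as evidence that early loss is expected or excused. None of them shows it.**

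- Schedule footnote 1 ("Loss to follow-up, or failure to attend the EOT visit due to a deteriorated clinical condition") belongs to the end-of-treatment visit, not the Week-12 scan.
- The row "Lost to follow-up" in SAP Table 10.2.4 is an empty shell for the whole study and says nothing about loss before Week 12.
- Listing 11.3.2 (censored patients, with a PFS3 column) is explained by toxicity stoppers without a PFS event and by patients still progression-free at cutoff.

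**The counts will be disclosed.** This stands in part. Table 10.1.1 and Listing 10.1.4 give treated and evaluable numbers and the reason for each non-evaluable patient, so a reader could assemble a figure such as 25/63. That is weaker than a pre-specified estimate with its interval.

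**Counting the lost as failures in the primary analysis would cost power.** This stands, and it rules out that remedy as a simple correction. If patients who stay have 50% PFS3 and the lost sit inside the 60 as No, the rate becomes 0.50·0.95 = 47.5% or 0.50·0.90 = 45.0%. Two-stage power then falls from 91.8% to 84.4% or 73.4%. It would also overturn the stated replacement design.

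**Conclusion.** The concern holds as a gap in the planned analyses. Treated patients with no Week-12 (or later) assessment and no listed failure leave the PFS3 denominator and are replaced. SAP 11.3.1 does not reach them, and no planned PFS3 rate includes them.

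The size is conditional. With a true all-treated rate of 30% and 2% to 10% lost, the chance of a positive result rises from 3.5% to between 4.5% and 10.8% if all lost patients are failures, or to between 4.0% and 6.4% if 15% are successes. It does not change if loss is unrelated to outcome. A reader might conclude that the false-positive rate is inflated; the documents do not establish this, because they give neither a loss rate nor its relation to outcome. The finding is that any such bias would not be visible in the planned PFS3 results.

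**What to change.** Keep the evaluable-patient primary analysis, the replacement rules and the 7/24 and 25/60 thresholds. Add to SAP 11.3.1 and Table 11.3.1 a pre-specified sensitivity row:

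*All Treated Patients; no documented progression-free status at Week 12 (or later) = PFS3 No; exact binomial estimate and 95% CI.*

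Report it beside the primary result, for example 25/60 = 41.7% (29.1–55.1) next to 25/63 = 39.7% (27.6–52.8).

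The cost is a sentence and one table row, with no additional patients or data. The companion estimate will be equal to or somewhat lower than the primary one whenever the added patients are scored No. It is conservative by construction and should be labeled as such.
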